9.4. SAFETYANALYSIS

Adverse events reported on case report forms will be mapped to preferred terms and organ systems using the MedDRA mapping system. For each preferred term event, frequency counts and percentages will be calculated by treatment period. Vital signs and clinical laboratory results will be descriptively summarized in terms of change from screening values.

9.5. SAMPLE SIZE

Twenty-four (24) subjects will be enrolled in this study. Sample size was determined by estimating the intrasubject variability for log-transformed data from previous studies of simufilam. A sample size of twenty four subjects is expected to provide 80% power to obtain 90% confidence intervals for the geometric mean ratios of C_{max} and the AUCs.

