## 1 INTRODUCTION

This document details the planned statistical analyses for *Cassava Sciences, Inc.*, protocol “PTI-125-05” study titled “A Four-way Crossover Food Effect and Bioequivalence Pharmacokinetic Study of Simufilam in Healthy Volunteers”.

The proposed analyses are based on the contents of the final version of the protocol (dated 05-MAR-2021)

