## 3 ENDPOINTS

### 3.1 Primary Endpoints

- $C_{max}$  - The maximum concentration determined directly from individual
- $T_{max}$  - Time to reach maximum concentration
- $AUC_{last}$  - Area under the curve to the time of the last quantifiable concentration, calculated using the linear trapezoidal method
- $AUC_{inf}$  - Area under the curve extrapolated to infinity
- $C_{last}$  - The last quantifiable concentration determined directly from individual concentration-time data
- $T_{last}$  - Time of the last quantifiable concentration
- $\lambda_z$  - The observed elimination rate constant; estimated by linear regression through at least three data points in the terminal phase of the log concentration-time profile
- $T_{1/2}$  - The observed terminal elimination half-life

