## 4 SAMPLE SIZE

Twenty-four (24) subjects (12 male and 12 female) will be enrolled in this study. Sample size was determined by estimating the intrasubject variability for log-transformed data from previous studies of simufilam. A sample size of twenty-four subjects is expected to provide 80% power to obtain 90% confidence intervals for the geometric mean ratios of  $C_{max}$  and the AUCs.

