## 6 PLANNED ANALYSES

No statistical analysis plan (SAP) prepared in advance of the data can be absolutely definitive and the final Clinical Study Report (CSR) may contain additional tables or statistical tests if warranted by the data obtained. The justification for any such additional analyses will be fully documented in the final CSR.

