### 6.3.1 Decimal Places

Derived data, where it is known in advance that the result will be an integer, such as age, will be presented with zero decimal places.

Mean and median will be displayed to one more decimal place than the data, standard deviation will have two more decimal places, and the minimum and maximum will be displayed to the same

QMD Ref: Worldwide-TMP-ST-006-4.0 Effective: 12Aug2019	Governing QMD: Worldwide-SOP-ST-001
Confidentiality Statement	

This document is the property of Worldwide Clinical Trials Inc. and may not be duplicated, copied, altered or removed from company without prior approval from Worldwide Quality Assurance or in compliance with Worldwide Standard Operating Procedures.

Worldwide Clinical Trials Controlled Quality Management Document			
 WORLDWIDE CLINICAL TRIALS	Sponsor:	Cassava Sciences, Inc	
	Protocol Number:	PTI-125-05	
STATISTICAL ANALYSIS PLAN – PHASE 1			

number of decimal places as reported in the raw data. Percentages will be displayed with one decimal place.

For PK data, individual concentrations and PK parameters will be reported to 3 significant figures. Time (hour) will also be presented in 3 significant figures. For summary statistics, n will be reported as a whole number; mean, SD, median, min, max, CV%, geometric mean, and geometric mean CV% will be reported to the same precision as for individual data (3 significant figures). For ANOVA results, geometric means, least squares means, and the difference in least squares means will be reported to 3 significant figures. Percent ratios of the geometric least squares means and associated 90% confidence intervals will be reported to 2 decimal places. CV% (intra-subject variability) will be presented to 2 decimal places.

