## **7 CHANGES TO PLANNED PROTOCOL ANALYSIS**

No changes to planned protocol analysis.

QMD Ref: Worldwide-TMP-ST-006-4.0 Effective: 12Aug2019	Governing QMD: Worldwide-SOP-ST-001
Confidentiality Statement	

This document is the property of Worldwide Clinical Trials Inc. and may not be duplicated, copied, altered or removed from company without prior approval from Worldwide Quality Assurance or in compliance with Worldwide Standard Operating Procedures.

Worldwide Clinical Trials Controlled Quality Management Document			
 WORLDWIDE CLINICAL TRIALS	Sponsor:	Cassava Sciences, Inc	
	Protocol Number:	PTI-125-05	
STATISTICAL ANALYSIS PLAN – PHASE 1			

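### Does an 80% power figure with no stated target leave the bioequivalence and food-effect conclusions to be chosen after the data?

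*Protocol*

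**What the plan says.** The sample-size text is the same in Protocol 9.5 and SAP 4. For Cmax and the AUCs alike, the planned number "is expected to provide 80% power to obtain 90% confidence intervals for the geometric mean ratios". Both say that the variability estimate came from earlier simufilam studies, and neither gives its value.

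Protocol 9.3 and SAP 6.10 set the analysis. Log-transformed AUClast, Cmax and, where the data allow, AUCinf enter a mixed model with sequence, period and treatment fixed and subject within sequence random. Three contrasts (high-fat vs fasted, low-fat vs fasted, Phase 2 vs current tablet fasted) are reported as geometric mean ratios with 90% confidence intervals. No acceptance limits are attached to any of them. SAP 7 adds nothing: "No changes to planned protocol analysis".

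Four other places bear on the question:
- SAP 1 gives the title as "A Four-way Crossover Food Effect and Bioequivalence Pharmacokinetic Study of Simufilam in Healthy Volunteers".
- SAP 3.1 places eight parameters under one primary heading, down to "The observed terminal elimination half-life".
- SAP 6.3.1 fixes the format: "Percent ratios of the geometric least squares means and associated 90% confidence intervals will be reported to 2 decimal places".
- SAP 6 notes that "the final Clinical Study Report (CSR) may contain additional tables or statistical tests if warranted by the data obtained", with the justification to be documented in that report.

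**The concern.** Power is the probability of an event, and obtaining an interval is not an event that can fail once the model fits. The 80% must therefore refer to something unnamed, most naturally an interval lying inside equivalence limits. The word Bioequivalence in the title points the same way. Yet neither document gives limits, says whether they would apply to the food contrasts as well as the tablets, or says which of the three exposure parameters must meet them.

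Add the SAP 6 allowance for further tests, and it seems that the rule for reading the intervals could be chosen once they are known. A 90% interval of 84-98% could be reported as a difference (it excludes 100%) or as equivalence (it lies inside 80-125%). One of 78-104% could be reported as no difference or as equivalence not shown. Both objectives would be touched: whether food alters exposure, and whether the two tablets match.

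**Working it through.** **1. Can the 80% be reproduced?** No. From the documents: 24 subjects, four periods, 90% intervals. Not in the documents, hence assumed: the limits, the true ratio and the within-subject CV. All 24 are taken to complete.

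Residual df = (24×4 − 1) − 23 − 3 − 3 = 66. On the log scale s_w = √ln(1+CV²), SE = s_w·√(2/24), and the interval is the estimate ± t(0.95, 66)·SE. Power is the probability that this interval lies within the limits, integrated over the chi-square distribution of the residual variance. Solving for the CV that gives exactly 80%:

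| Assumed limits | True ratio 1.00 | True ratio 0.95 |
|---|---|---|
| 90-111% | 12.4% | 7.5% |
| 80-125% | 26.6% | 23.7% |
| 75-133% | 34.7% | 32.4% |
| 70-143% | 43.7% | 41.8% |

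The statement fits CVs from 7.5% to 43.7%. It neither reveals a hidden rule nor can be shown wrong. With 80-125% and a true ratio of 0.95, power is 90.7%, 75.8% and 58.2% at CV 20%, 25% and 30%, so 24 subjects may be ample or short depending on a CV that is not given.

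**2. What is actually left open?**

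| Element | Fixed in advance? | Where |
|---|---|---|
| Scale, model, interval level | Yes | Protocol 9.3, SAP 6.10 |
| Contrasts and reference treatments | Yes | Protocol 9.3, SAP 6.10 |
| Parameters analysed | Yes: Cmax, AUClast, AUCinf | SAP 6.10; Tables 14.4.3 and 14.4.4 |
| When AUCinf counts | Yes: adjusted R² at least 0.80, extrapolation under 30% | SAP 6.2.10 |
| Limits, and which parameters must meet them | No | - |

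Of the eight parameters called primary, Tmax, Clast, Tlast, λz and half-life have no planned test. The list is a loose label and does not add to what is tested.

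**3. Does SAP 6 create the problem?** Strike out its sentence on added tests, and the limits are still missing. It allows documented additions. It says nothing about how the planned intervals are to be read.

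**4. Do two readings of one interval contradict each other?** At CV 20%, s_w = √ln(1.04) = 0.198 and SE = 0.198 × 0.2887 = 0.0572, so the interval is the estimate multiplied and divided by 1.10. An observed ratio of 1.12 gives 1.018 to 1.232. This is a difference and it lies within 80-125%. Both statements are true together. At CV 25% the factor is 1.126 and the interval is 0.995 to 1.261: no difference shown and equivalence not shown, which is an inconclusive result.

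With 80-125% and a true ratio of 0.95, the chance that one of these two patterns occurs is 54.7%, 31.2%, 13.9%, 8.5% and 25.8% at CV 10%, 15%, 20%, 25% and 30%. At CV 20% or below almost all of it is the first pattern. At 30% all of it is the second. These figures therefore do not measure the risk of opposite conclusions. The competing rule, that the interval excludes 100%, appears in neither document.

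**The case for a change.** The best case for a change is that an estimation study needs no limits, but this one carries Bioequivalence in its title and quotes a power, and both presuppose a criterion. Limits of 80-125% may be what everyone has in mind, yet they are not written, and neither is the set of parameters that must pass. That set can matter. Assume 80-125%, a true ratio of 0.95 for both parameters and an AUC CV of 15%. Then AUC passes while Cmax fails in 8-9%, 23-24% or 41-42% of trials at Cmax CV 20%, 25% or 30%, whatever their correlation. A justification in the study report gives openness after the fact, not a rule set beforehand. Writing the rule down would cost a few sentences.

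Part of this stands. The power sentence is incomplete, and a formal bioequivalence claim for the two tablets would rest on limits that the plan does not name. It goes no further than that. The objectives speak of assessing and comparing, and Protocol 4 of estimating the food effect and of relative bioavailability, so no text promises a yes-or-no verdict on food. Table 14.4.4 is planned for the systemic exposure parameters as a group, so a Cmax interval that misses a limit would be reported with the AUC intervals. The Cmax figures depend on assumed CVs and show no fault in the chosen sample size.

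**Conclusion.** No change is called for. The power sentence is badly worded and leaves out its inputs. That is a gap in documentation, and it alters no estimate, interval, contrast or analysis set. A stated rule and an estimation-only reading would lead to the same tables. Since ratios and 90% intervals are reported to two decimals, any reader can hold them against whatever limits apply, and a report that claims bioequivalence would have to name its limits to be understood.

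The size of the gap is this: the 80% is compatible with CVs of 7.5% to 43.7% over the limits tried, so it is uninformative but not shown to be false. Whatever the true value, precision with 24 completers is set by the CV alone: the interval is the estimate multiplied and divided by about 1.05, 1.07, 1.10, 1.13 or 1.15 at CV 10%, 15%, 20%, 25% or 30%. All limits, CVs and true ratios used here are assumptions. If the earlier-study CV were above 23.7%, and equivalence within 80-125% at a true ratio of 0.95 were the aim, 24 completers would give less than 80%. Nothing in the documents shows that either condition holds.

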10. STUDY TERMINATION

The study will be terminated following completion of the study or at any time at the discretion of the Sponsor.

11. DATA COLLECTION, RETENTION AND MONITORING

11.1. CASE REPORT FORMS

Case report forms (CRFs) will be provided for each subject. The subjects in the study will not be identified by name on any study documents to be collected by the Sponsor (or CRO designee), but will be identified by a Study Identification Number and initials.

All clinical information requested in this protocol will be recorded on the CRFs provided by the Sponsor using legible entries with a black ballpoint pen. If an error is made, a single line will be drawn through the error and the correct response will be written adjacent to the error, and initialed and dated.

CRFs must be reviewed and verified for accuracy by the Principal Investigator and signed-off before collection by the Sponsor (or CRO designee). A copy of the CRF will remain at the Investigator's site at the completion of the.

11.2. AVAILABILITY AND RETENTION OF INVESTIGATIONAL RECORDS

The Investigator must make study data accessible to the monitor, other authorized representatives of the Sponsor (or designee) and Regulatory Agency (e.g., FDA) inspectors upon request. To assure accuracy of data collected in the CRFs, it is mandatory that Sponsor representatives have access to original source documents (e.g., subject records, subject charts, and laboratory reports). During review of these documents, the subject's anonymity will be maintained with adherence to professional standards of confidentiality and applicable laws. A file for each subject must be to that subject. The Investigator must ensure the reliability and availability of source documents from which the information on the CRF was derived. Investigators are

required to maintain all study documentation until notification by PTI that any records may be discarded.

The Investigator is responsible for maintaining adequate case histories in each subject's source records. The Sponsor reserves the right to terminate the study for the Investigator's refusal to supply source documentation of work performed in this clinical trial.

11.3. SUBJECT CONFIDENTIALITY

All reports and subject samples will be identified only by Study Identification Number and initials to maintain subject confidentiality. Additional subject confidentiality issues (if applicable) are covered in the Clinical Study Agreement.

11.4. LIABILITY

In the event of a side effect or injury, appropriate medical care as determined by the Investigator or his/her designated alternate will be provided.

If a bodily injury is sustained, resulting directly from the use of the study drug, the Sponsor will reimburse for reasonable physician fees and medical expenses necessary for treatment of only the bodily injury which is not covered by the subject's medical or hospital insurance, provided that the injury is not due to a negligent or wrongful act or omission by the study doctor and his/her staff. No other compensation of any type will be provided by the study Sponsor. Financial compensation for lost wages, disability or discomfort due to the study is not available.

11.5. ETHICAL AND LEGAL ISSUES

The Investigator and site personnel are responsible for conducting this study in accordance with the ICH, GCP, and all other applicable laws and regulations.

11.5.1. Institutional Review Board

The protocol and Informed Consent Form must be approved by an IRB before the study is initiated. The IRB must comply with U.S. CFR 21 Part 56 and local laws.

Documentation of IRB approval must be provided to the Sponsor. Investigators are responsible for the following:

 Obtaining IRB approval of the protocol, Informed Consent Form, and any advertisements to recruit patients and IRB approval of any protocol amendments and Informed Consent Form revisions before implementing the changes.

- Providing the IRB with any required information before or during the study.
- Submitting progress reports to the IRB, as required, requesting additional review and approval, as needed; and providing copies of all relevant IRB communications to the Sponsor.
- Notifying the IRB within 15 calendar days of all SAEs and unexpected AEs related to study medications reported by the Sponsor to the Investigator.

11.6. INFORMED CONSENT FORM

The Sponsor (or designee) must review the Investigator's proposed Informed Consent Form prior to IRB submission for approval. An IRB-approved copy of the Informed Consent Form will be forwarded to the Sponsor.

The Informed Consent Form documents study-specific information the Investigator provides to the subject and the subject's agreement to participate. The Investigator explains in plain terms the nature of the study along with the aims, methods, anticipated benefits, potential risks, and any discomfort that participation may entail. The Informed Consent Form must be signed and dated before the subject enters the study. The original Informed Consent Form and any amended Informed Consent Form, signed and dated, must be retained in the subject's file at the study site and a copy must be given to the subject.

12. INVESTIGATOR RESPONSIBILITIES

The Investigator agrees to:

- Conduct the study in accordance with the protocol, except to protect the safety, rights, or welfare of patients.
- Personally conduct or supervise the study.
- Ensure that requirements for obtaining informed consent comply with ICH, CFR 21 Parts 50 and 56 and local laws.
- Report to the Sponsor any AEs that occur during the study in accordance with ICH, CFR 21 Part 312.64 and local laws.
- Read and understand the Investigator's Brochure including potential risks and side effects of the drug.
- Ensure that all associates, colleagues, and employees assisting in the conduct of the study are informed about their obligations in meeting the above commitments.

- Maintain adequate records in accordance with ICH, 21 CFR Part 312.62, and local laws and have records available for inspection by the Sponsor, FDA, or other authorized agency.
- Promptly report to the IRB and the Sponsor all changes in research activity and unanticipated problems involving risks to patients or others (including amendments and expedited safety reports).
- Comply with all other requirements regarding obligations of Clinical Investigators and all other pertinent requirements listed in ICH, 21 CFR Part 312 and local laws.

14. APPENDIX A – SCHEDULE OF ACTIVITIES

Procedure	SCREENING (Days -28 to Day -1)	DAY 0 CHECK-IN	DAY 1 Time = 0	DAY 2 4 & 6	DAY 3 5 & 7	DAY 8 DISCHARGE
Informed Consent	X					
COVID-19		X				
Medication and medical histories	X	X				
Ethanol urine test	X	X				
Urine drug screen/ Urine cotinine	X	X				
Pregnancy test		X				
Review of inclusion/ exclusion criteria	Х	X				
Drug administration			X		X	
Physical examination	X					X
ECG	X					X
Biochemistry, hematology, urinalysis	X		X			X
HCV, HBsAG & HIV screen	X					
Adverse events			X	X	X	X
Vital signs	X		X	X	X	X
Blood sample collection for PK analysis			X	X	X	X

## SAP Amendments before database lock

Version	Issue Date	Section	Revision / Addition	Rationale
-	-	-	-	-

QMD Ref: Worldwide-TMP-ST-006-4.0 Effective: 12Aug2019	Governing QMD: Worldwide-SOP-ST-001
Confidentiality Statement	

This document is the property of Worldwide Clinical Trials Inc. and may not be duplicated, copied, altered or removed from company without prior approval from Worldwide Quality Assurance or in compliance with Worldwide Standard Operating Procedures.

Worldwide Clinical Trials Controlled Quality Management Document			
 WORLDWIDE CLINICAL TRIALS	Sponsor:	Cassava Sciences, Inc	
	Protocol Number:	PTI-125-05	
STATISTICAL ANALYSIS PLAN – PHASE 1			

## 1 INTRODUCTION

This document details the planned statistical analyses for *Cassava Sciences, Inc.*, protocol “PTI-125-05” study titled “A Four-way Crossover Food Effect and Bioequivalence Pharmacokinetic Study of Simufilam in Healthy Volunteers”.

The proposed analyses are based on the contents of the final version of the protocol (dated 05-MAR-2021)

## 2 STUDY OBJECTIVES

The objectives of this study are

1. to assess the effect of food on the rate and extent of absorption of simufilam
2. to compare the pharmacokinetic profile of the Phase 3 formulation of simufilam to that of the earlier Phase 2 formulation.

## 3 ENDPOINTS

### 3.1 Primary Endpoints

- $C_{max}$  - The maximum concentration determined directly from individual
- $T_{max}$  - Time to reach maximum concentration
- $AUC_{last}$  - Area under the curve to the time of the last quantifiable concentration, calculated using the linear trapezoidal method
- $AUC_{inf}$  - Area under the curve extrapolated to infinity
- $C_{last}$  - The last quantifiable concentration determined directly from individual concentration-time data
- $T_{last}$  - Time of the last quantifiable concentration
- $\lambda_z$  - The observed elimination rate constant; estimated by linear regression through at least three data points in the terminal phase of the log concentration-time profile
- $T_{1/2}$  - The observed terminal elimination half-life

## 4 SAMPLE SIZE

Twenty-four (24) subjects (12 male and 12 female) will be enrolled in this study. Sample size was determined by estimating the intrasubject variability for log-transformed data from previous studies of simufilam. A sample size of twenty-four subjects is expected to provide 80% power to obtain 90% confidence intervals for the geometric mean ratios of  $C_{max}$  and the AUCs.

## 5 RANDOMIZATION

QMD Ref: Worldwide-TMP-ST-006-4.0 Effective: 12Aug2019	Governing QMD: Worldwide-SOP-ST-001
Confidentiality Statement	

This document is the property of Worldwide Clinical Trials Inc. and may not be duplicated, copied, altered or removed from company without prior approval from Worldwide Quality Assurance or in compliance with Worldwide Standard Operating Procedures.

Worldwide Clinical Trials Controlled Quality Management Document									
 WORLDWIDE CLINICAL TRIALS					Sponsor:		Cassava Sciences, Inc		
					Protocol Number:		PTI-125-05		
STATISTICAL ANALYSIS PLAN – PHASE 1									

Subjects will be randomly assigned to one of four treatment sequences (6 subjects/sequence) to receive a single oral dose of simuflam in each treatment period either under fasted condition or low fat fed condition or high fat fed condition or phase 2 tablet as shown in Table 1.

The administration of each dose of study drug will be separated by a 48-hour washout period. PK blood samples will be obtained prior to dosing and at specified intervals during the study (0-48 h post-dose for Treatment Periods 1 - 4). The observation period for safety will continue through the incarceration period.

**Table 1 Treatment Sequences by Period**

Sequence	Treatment Period -1				Treatment Period -2				Treatment Period -3				Treatment Period -4			
	Fasted	High	Low	Phase 2 Tablet	Fasted	High	Low	Phase 2 Tablet	Fasted	High	Low	Phase 2 Tablet	Fasted	High	Low	Phase 2 Tablet
Sequence A (n = 6)				X			X		X					X		
Sequence B (n = 6)	X							X		X					X	
Sequence C (n = 6)		X			X						X					X
Sequence D (n = 6)			X			X						X	X			

